6.0 STUDY POPULATION

A required number of healthy volunteers, male and non-pregnant female, aged between 18 and 55 years of age will be screened according to the inclusion and exclusion criteria listed in [Sections 7.3](#) and [7.4](#) to be sure that about 65-66 are randomized. The volunteers will be selected at the participating clinical site.

This study will be conducted in normal, healthy male and non-pregnant female volunteers, as intended for general population³. No one racial group will exceed 65% of total enrolled subjects.

To assure subjects' safety, eligibility will be assessed at the time of screening and upon entry into the clinic prior to first drug administration.

7.0 SUBJECT SELECTION AND WITHDRAWAL/TERMINATION

7.1 Sample Size

A sample size of 65-66 subjects (minimum of 52 subjects to complete the study) is estimated to attain at least 80% statistical power to demonstrate 2x2 crossover bioequivalence study with a margin of 80-125% between the Test and Reference products, assuming the mean Test to Reference difference is within 5% Type I error and the geometric mean ratio is 1.08, based on an estimated intra-subject variability of approximately 27%. Subjects who are dosed will not be replaced.

The subjects will be dosed in two or more groups.

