5.3 Randomization and Blinding

In this study, the assignment of study arm groups (randomization scheme) will be generated by a computer program designed and run in SAS[®] Version 9.4 [REDACTED]. This is an open-label study and subjects as well as clinic staff will not be blinded to the randomization. The bioanalytical laboratory will not have access to the randomization scheme until the bioanalytical analysis is complete.

Subjects who meet the eligibility criteria will be randomly assigned equally into one of the following four sequence groups:

	Period 1	Period 2	Period 3	Period 4
Sequence 1	A	B	C	D
Sequence 2	B	C	D	A
Sequence 3	C	D	A	B
Sequence 4	D	A	B	C

Each subject is scheduled to receive four periods by the end of the study (See Appendix A).

Study arm A (Test): Nifedipine extended-release tablets [REDACTED]
[REDACTED] 60 mg

Study arm B (Reference): PROCARDIA XL extended-release tablets [REDACTED]
60 mg

Study arm C (PPI/antacid + Test): omeprazole/sodium bicarbonate capsules, 40 mg/1100 mg + Nifedipine extended-release tablets [REDACTED],
[REDACTED], 60 mg.

Study arm D (PPI/antacid + Reference): omeprazole/sodium bicarbonate capsules, 40 mg/1100 mg + PROCARDIA XL extended-release tablets [REDACTED] 60 mg.

The trial will be performed as an open-label study as the pharmacokinetic profile should not be expected to be affected by having the knowledge of reference or generic nifedipine ER tablets was administered. Blinding of the subjects as well as clinic staff is not considered necessary. Only the bioanalytical laboratory staff will not have access to the randomization scheme until the bioanalytical analysis is complete.

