13.3.3 Statistical Analysis

Descriptive statistics (min, max, median, mean, standard deviation and coefficient of variability) of all PK parameters will be provided for nifedipine for all study arm groups.

ANOVA including sequence, subjects nested within sequence, period and study arm will be performed on the ln-transformed data for AUC_t , AUC_{inf} and C_{max} and on the untransformed data for T_{max} , λ and $T_{1/2}$.

T_{max} will be analyzed using an additional non-parametric test (Wilcoxon test).

The 90% CI of the ratios of geometric means for AUC_t , AUC_{inf} and C_{max} will be calculated based on the LSMEANS and ESTIMATE of the ANOVA.

The following PK comparisons will be carried out:

- Test with PPI (Study arm C)/Test without PPI (Study arm A)
- Reference with PPI (Study arm D)/Reference without PPI (Study arm B)
- Test with PPI (Study arm C)/Reference with PPI (Study arm D)
- Test without PPI (Study arm A)/Reference without PPI (Study arm B)

For Pharmacodynamic Data:

The descriptive statistics (min, max, median, mean, standard deviation and coefficient of variability) of the gastric pH and change of gastric pH will be calculated for both test and reference products.

Analysis of Variance (ANOVA) for gastric pH and change of gastric pH from baseline will be carried out.

The following gastric pH comparisons will be carried out:

- Study arm C PPI (Day7) – Study arm A (Day2)

- Study arm D_{PPI (Day7)} – Study arm B_(Day2)
- The comparison of the change between test and reference can be assessed

Additional statistical and alternate tests will be performed if necessary.

Missing data will not be included in the statistical analysis. There are potential two kinds of unbalanced designs for the analysis: (1) unequal number of subjects across groups, (2) missing cells: there are not available data for some subjects. The Type 3 method will be used for the calculation of sums of squares using SAS software. All the fixed effects will be tested using the Type 3 in the ANOVA to detect statistically significant differences ($\alpha=0.05$) if applicable. A mixed effects ANOVA model for gastric pH with fixed factors of sequence, period, and study arm and random effects of subject will be fit. A compound-symmetric or other appropriate covariance structure will be used in the analysis.

The null hypotheses for gastric pH comparisons for different study arms are:

- For the comparison of Study Arm A and Study Arm C

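### Dosing in two or more groups is planned, but neither the PK ANOVA nor the gastric pH model has a period-within-group term, and balance of sequences within group is not stated

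*Combined protocol and SAP*

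**What the plan says.** - **Groups.** Section 7.1 says "The subjects will be dosed in two or more groups", and the synopsis repeats it. The number, size and dates of the groups are not given.
- **PK model.** Section 13.3.3: "ANOVA including sequence, subjects nested within sequence, period and study arm will be performed on the ln-transformed data". There is no group, period-within-group or group-by-arm term.
- **Gastric pH model.** The mixed model in the same section has fixed sequence, period and study arm and a random subject effect. It has no group term either.
- **Randomization.** Section 5.3: "Subjects who meet the eligibility criteria will be randomly assigned equally into one of the following four sequence groups". Blocking or stratification by dosing group is not mentioned. Part of the text on generating the scheme is redacted.
- **General clauses.** Sections 13.3 and 13.3.3 allow justified changes and additional tests. Section 13.3.3 also mentions unequal numbers across groups, but only as a reason for Type 3 sums of squares. None of these names an effect of dosing group.

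**The concern.** If the groups are dosed at different times, Period 2 in one group is not the same occasion as Period 2 in another. A model with a single period effect assumes that both groups share it. Any departure from that assumption is known design structure left in the residual, and the residual sets the width of every 90% confidence interval compared with 80.00-125.00%. Those intervals decide all four PK comparisons. If sequences also happen to be unbalanced within group, part of a group-by-period shift is confounded with study arm and moves the estimate in the trial actually run. The planned output would show neither effect.

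**Working it through.** **Are the groups staggered?** The Appendix A example runs 68 days for one subject, after up to 28 days of screening: 68 + 28 = 96 days, or 13.7 weeks. The synopsis allows 13 to 19 weeks. Nineteen weeks is 133 days, which leaves up to 133 - 96 = 37 days for staggered starts. Section 5.2 says about 9 weeks (63 days), which is shorter than the 68-day example. Staggering is therefore a fair inference, but the two durations must be reconciled.

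**The plan's own figure.** Section 7.1 gives "A sample size of 65-66 subjects", "minimum of 52 subjects to complete the study" and "is estimated to attain at least 80% statistical power". It assumes a ratio of 1.08 and is "based on an estimated intra-subject variability of approximately 27" percent.
- Log-scale SD: σ = sqrt(ln(1 + 0.27²)) = 0.265.
- SE of an arm contrast with 52 completers: 0.265 × sqrt(2/52) = 0.0520.
- Power of the two one-sided tests at 0.05: 87.0% with 50 df (2x2 design) and 87.5% with 150 df (four-period model). The claim of at least 80% is met.

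**Degrees of freedom.** For G groups, the residual df with period within group is 3n - 3G - 3. At n = 52 this is 150, 147, 144 and 141 for one to four groups. Power is 87.5% in each case. At 65-66 subjects it stays at 93.1-93.4%.

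**Loss of precision under the planned model.** Take two groups of 26 with balanced sequences, and let each group-period cell carry an independent shift with SD τ. The expected group-by-period sum of squares is 52 × 3 × τ²/2 = 78τ². Spread over 150 df, this adds 0.52τ² to σ² = 0.0704. The half-width is therefore multiplied by about sqrt(1 + 0.52τ²/0.0704). The documents give no value for τ, so a range is shown.

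| Assumed τ | Formula | Simulated half-width, with / without period within group | Planned CI wider by (reciprocal of simulated ratio) |
|---|---|---|---|
| 0 | 1.000 | 1.000-1.002 | none (0-0.2% narrower) |
| 0.05 | 1.009 | 0.991-0.992 | 0.8-0.9% |
| 0.10 | 1.036 | 0.963-0.966 | 3.5-3.8% |
| 0.15 | 1.080 | 0.929-0.931 | 7.4-7.6% |

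The formula runs slightly high at τ = 0.15 because it takes the root of a mean variance rather than the mean of roots. With no shift and sequences unbalanced within group, adding the term widens the interval by about 1% (1.4% in one unbalanced split).

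**Power at a true ratio of 1.08** (simulated, Monte Carlo error about 1 point):

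| Assumed τ | Planned model, unbalanced within group | Planned model, balanced within group | With period within group |
|---|---|---|---|
| 0.1 | 84.5% | 86.2% | 87.6-88.1% |
| 0.2 | 78.8% | 82.5% | 87.5-87.7% |

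**Validity.** At a true ratio of 1.25 the planned model rejected in 4.1-5.0% of trials, and mean estimates were unbiased. Without balance within group, the shift in a single trial's A/B log-ratio reached about 0.027 (τ = 0.10) or 0.058 (τ = 0.20) at the 95th percentile. Balancing removed it.

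**The case against.** The strongest reply is that the effect is small, conservative and built on an assumed shift.
- A constant difference between groups is absorbed by the subject effects, so only a group-by-period interaction matters.
- The study has one centre (Section 5.1) and standardized meals (Section 8.2), and it assumes low inter-occasion physiological variability (Section 3.2). Nothing points to large shifts.
- At 52 completers the half-width is 1.655 × 0.0520 = 0.0861. At a ratio of 1.08 the upper limit is 1.08 × exp(0.0861) = 1.177. A half-width 3.6% or 7.4% larger gives 1.181 or 1.185, still well inside 1.25.

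All of this stands and limits the size of the point. It does not show that the planned model is preferable, because the added term costs almost nothing.

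A reader might also infer more than the documents support:
- **Randomization is not blocked by group.** Section 5.3 is silent beside a redaction. Only the absence of a statement can be reported. A stated rule would still help: 65 = 4 × 16 + 1 and 66 = 4 × 16 + 2, so exactly equal allocation to four sequences is impossible even overall.
- **Ignoring groups always widens the intervals.** With no shift, the planned intervals are equal or very slightly narrower.
- **The trial risks false equivalence.** Neither average bias nor type I error inflation appeared.
- **The trial is underpowered.** Power fell below 80% only at τ = 0.2 with sequences unbalanced within group.

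The general clauses on extra analyses do not close the gap, since they name no group effect and could be used after the data are seen.

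**Conclusion.** The gap is real and modest. Grouped dosing is planned, both models ignore it, and balance of sequences within group is not stated. The consequence is lost precision: 90% intervals about 1%, 4% and 7% wider than needed for assumed shift SDs of 0.05, 0.10 and 0.15. In a trial with sequences unbalanced within group, the realised arm contrast may also move.

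These sizes assume two equal groups, 52 completers, a CV of 27%, independent shifts in each group and period, and (for the interval widths) sequences balanced within group. That dosing dates differ is inferred from the synopsis duration, which conflicts with Section 5.2. The effect on the gastric pH comparisons cannot be sized, because no variance is given for pH. The validity of the equivalence tests is not in question.

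**What to change.** - In Section 13.3.3, pre-specify for the PK parameters: group, sequence, group x sequence, subject within group x sequence, period within group, and study arm. Period within group is the term that changes the intervals. With fixed subject effects, group and group x sequence leave the arm contrasts unchanged.
- Apply the same structure to the gastric pH mixed model.
- In Section 5.3, define the dosing groups and state that sequences are balanced within each, for example by blocks of four.
- Report group x arm descriptively, not as a gate on pooling. If pooling were refused, one group of 26 would have 60% power and one of 33 would have 70% (2x2 df).
- Reconcile the 13 to 19 weeks in the synopsis with the 9 weeks in Section 5.2.

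The cost is analysis wording and, if not already in place, a blocked randomization list. Statistically it takes 3 residual df per extra group. If there is no shift, intervals are about 0% wider with balanced sequences and about 1% wider with unbalanced ones. No additional subjects are needed.

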7.2 Inclusion Criteria

Potential subjects meeting all of the following criteria may be included in the study:

1. Healthy, males and non-pregnant (excluding nursing and lactating) female volunteers, 18 to 55 years of age, inclusive.
2. Smoking status: Only non-tobacco/nicotine users (for at least 6 months prior to the clinical study) will be eligible to participate in this study.
3. BMI that is within 18.5-35.0 kg/m², inclusive.
4. Healthy, according to the medical history, ECG, vital signs, laboratory results and physical examination as determined by the PI/Sub-Investigator.
5. Ability to comprehend and be informed of the nature of the study, as assessed by BPSI staff. Capable of giving written informed consent prior to receiving any study procedure. Must be able to communicate effectively with clinic staff.
6. Ability to fast for at least 14 hours.
7. Availability to volunteer for the entire study duration and willing to adhere to all protocol requirements.
8. Female subjects must fulfill at least one of the following:
 - Be surgically sterile for a minimum of 6 months;
 - Post-menopausal for a minimum of 1 year;
 - Agree to avoid pregnancy and use medically acceptable method of contraception from at least 30 days prior to the study until 30 days after the study has ended (last study procedure).

Medically acceptable methods of contraception include contraceptives, intrauterine device, or double barrier method (condom with foam or vaginal spermicidal suppository, diaphragm with spermicide). Complete abstinence alone can be used as a method of contraception.

7.3 Exclusion Criteria

Potential subjects meeting any of the following criteria will be excluded:

1. Known history or presence of any clinically significant hepatic, renal/genitourinary, gastrointestinal (e.g., gastrointestinal obstruction, gastrointestinal ulcers), cardiovascular (e.g., severe obstructive coronary artery disease, myocardial infarction, angina, heart failure), cerebrovascular, pulmonary, endocrine, immunological, musculoskeletal, neurological, psychiatric, dermatological or hematological disease or condition unless determined as not clinically significant by the PI/Sub-Investigator.
2. Clinically significant history or presence of any clinically significant gastrointestinal pathology (e.g. chronic diarrhea, inflammatory bowel disease), unresolved gastrointestinal symptoms (e.g. diarrhea, vomiting, swallowing disorder), or other conditions known to interfere with the absorption, distribution, metabolism or excretion of the drug experienced within 7 days prior to first dosing, as determined by the PI/Sub-Investigator.
3. QTc interval > 430 milliseconds for males and > 450 milliseconds for females, unless deemed otherwise by the PI/Sub-Investigator.
4. Abnormal clinical laboratory values, unless values are deemed by the PI/Sub-Investigator as “Not Clinically Significant”.
5. Hemoglobin values less than 11.5 g/dl.
6. Abnormal vital signs (blood pressure [BP], heart rate [HR], respiratory rate [RR] and temperature) measurements, unless deemed otherwise by the PI/Sub-Investigator.
7. Presence of any clinically significant illness within 30 days prior to first dosing, as determined by the PI/Sub-Investigator.
8. Presence of any significant physical or organ abnormality as determined by the PI/Sub-Investigator.
9. Individuals who have implanted or portable electro-mechanical medical device such as a cardiac pacemaker, defibrillator or infusion pump.

10. A positive test result for any of the following: HIV, Hepatitis B surface antigen, Hepatitis C, drugs of abuse (marijuana, amphetamines, barbiturates, cocaine, opiates, phencyclidine and benzodiazepines), alcohol test and cotinine. Positive pregnancy test for female subjects.
11. Known history or presence of:
 - Alcohol abuse or dependence within one year prior to first study period;
 - Drug abuse or dependence;
 - Hypersensitivity or idiosyncratic reaction to nifedipine, omeprazole/sodium bicarbonate, its excipients, and/or related substances;
 - Hypotension;
 - Bartter's syndrome;
 - Gastric bezoar;
 - Crohn's disease or diverticulitis;
 - severe dysphagia to food or pills;
 - Food allergies and/or presence of any dietary restrictions;
 - Severe allergic reactions (e.g. anaphylactic reactions, angioedema).
12. History of intolerance to and/or difficulty with blood sampling through venipuncture.
13. Abnormal diet patterns (for any reason) during the four weeks preceding the study, including fasting, high protein diets, vegan, etc.
14. Individuals who have donated, in the days prior to first study period:
 - 50-499 mL of blood in the previous 30 days;
 - 500 mL or more in the previous 56 days.
15. Donation of plasma by plasmapheresis within 7 days prior to first study period.
16. Individuals who have participated in another clinical trial or who received an investigational drug within 30 days prior to first study period.
17. Use of any enzyme-modifying drugs and/or other products, including strong inhibitors of cytochrome P450 (CYP) enzymes (e.g. cimetidine, fluoxetine, quinidine, fluconazole, ketoconazole, voriconazole,

itraconazole, clarithromycin, erythromycin, nefazodone, atazanavir, saquinavir, indinavir, and nelfinavir) and strong inducers of CYP enzymes (e.g. barbiturates, carbamazepine, glucocorticoids, phenytoin, St. John's Wort and rifampin) in the previous 30 days before first study period.

18. Use of drugs such as, proton pump inhibitors, clopidogrel, tacrolimus, digoxin, cyclosporine, disulfiram, benzodiazepines, diazepam, warfarin, methotrexate, iron salts, erlotinib, and mycophenolate mofetil (MMF) in the previous 30 days before first study period, or individuals with vitamin B-12 deficiency (as long-term dosing (more than 3 years) of omeprazole/sodium bicarbonate may lead to vitamin B-12 deficiency)
19. Individuals having undergone gastrointestinal (GI) surgery within 3 months prior to first study period, unless deemed otherwise by PI/Sub-Investigator.
20. Use of any prescription medication within 14 days prior to first study period (except for contraceptives).
21. Use of any over-the-counter medications (including oral multivitamins, herbal and/or dietary supplements and/or teas) within 14 days prior to first study period (except for spermicidal/barrier contraceptive products).
22. Consumption of food or beverages containing grapefruit and grapefruit juice and/or pomelo within 10 days prior to first study period.
23. Consumption of food or beverages containing caffeine/methylxanthines, poppy seeds and/or alcohol within 48 hours before dosing.
24. Use of diuretics (drugs or food, see [Appendix D](#)) within 24 hours before dosing of SmartPill™.
25. Individuals having undergone any major surgery within 6 months prior to the start of the study, unless deemed otherwise by PI/Sub-Investigator.
26. Difficulty with swallowing whole tablets or large capsules.
27. Have had a tattoo or body piercing within 30 days prior to first study period and during the study.

7.4 Informed Consent Procedure

The Investigator is responsible for ensuring that the informed consent is obtained before any protocol specific procedures are carried out. The decision of a subject to participate in clinical research is voluntary and should be based on a clear understanding of what is involved.

Subjects must receive adequate oral and written information. The oral explanation to the participant should be performed by the Investigator or a designated person, and must cover all the elements specified in the informed consent form.

The subject must be given every opportunity to clarify any points they do not understand and, if necessary, to ask for more information. The subject must be given sufficient time to consider the provided information. It should be emphasized that the subjects may withdraw their consent to participate at any time without loss of benefits to which they otherwise would be entitled.

The subjects should be informed and agree that their names will not be disclosed outside the site.

The Investigator or delegated member of the trial team and the subject should sign and date the Informed Consent Form to confirm that consent has been obtained. The participant should receive a copy of this document and the original should be filed in the subject binder. In case of a screen failure, it will be filed separately in the designated binder.

7.5 Screening Procedures

Subjects will review and sign the ICF prior to medical screening procedures. Screening procedures will be conducted within thirty (30) days prior to dosing in Period 1. Screening procedures can be performed on the day of check-in prior to conducting check-in procedures. The physician (Principal Investigator (PI) or Sub-Investigator) will review all screening results/data to assess eligibility of each potential subject.

The Screening procedures will include (but is not limited to): demographic data, medical and medication histories, physical examinations, body measurements, vital signs (seated blood pressure [BP], heart rate [HR], respiratory rate [RR] and temperature.), electrocardiogram (ECG), hematology, biochemistry, serology, urinalysis, urine screening for drugs of abuse and cotinine, alcohol test and serum pregnancy test (female subjects only). For a complete listing of all tests to be performed, please refer to [Appendix B - Clinical Laboratory Assessment](#).

7.6 Study Restrictions

If any subject does not comply with these restrictions, at any time prior to or during the study, continued participation will be re-assessed by the PI/Sub-Investigator, BPSI PK Scientist and/or the Sponsor.

1. No food will be allowed from at least 8 hours before dosing until at least 6 hours after dosing (Study arm A and B). Following the administration of omeprazole/sodium bicarbonate capsules on Day 6, subjects will be required

to fast for at least an 8-hour overnight fasting period before dosing of nifedipine together with omeprazole/sodium bicarbonate capsules on Day 7, and will continue to fast for at least 6 hours after dosing (Study arm C and D). Except for water given with study medication (nifedipine, omeprazole/sodium bicarbonate, SmartPill™), no fluid will be allowed from 8 hours before dosing until 6 hours post-dose. Water will be allowed up to ½ cup (4 fl. oz.) during the six (6) hours post-dose and then water will be allowed/provided *ad libitum* at all other times.

2. For Study arm C and D, no food will be allowed from at least 8 hours before dosing of omeprazole/sodium bicarbonate capsules from Day 1 to Day 6 until at least 1 hour after dosing. Except for water given with study medication, no fluid will be allowed from 1 hour before dosing and 1 hour post-dose. Water will be allowed up to ½ cup (4 fl. oz.) during the six (6) hours post-dose and then water will be allowed/provided *ad libitum* at all other times.
3. Subjects will be required to abstain from smoking or use of tobacco products from 6 months prior to the first study period and for the entire duration of the study based on self-reporting and the cotinine test.
4. Use of any enzyme-modifying drugs and/or other products, including strong inhibitors of cytochrome P450 (CYP) enzymes (e.g., cimetidine, fluoxetine, quinidine, fluconazole, itraconazole, clarithromycin, erythromycin, nefazodone, saquinavir, indinavir, and nelfinavir) and strong inducers of CYP enzymes (e.g., barbiturates, carbamazepine, glucocorticoids, phenytoin, St. John's Wort and rifampicin) within 30 days prior to first study period until the last blood draw in the final study period.
5. Use of drugs such as, proton pump inhibitors, clopidogrel, tacrolimus, digoxin, cyclosporine, disulfiram, benzodiazepines, diazepam, warfarin, methotrexate, iron salts, antibiotics containing ampicillin, erlotinib, and mycophenolate mofetil (MMF) in the previous 30 days before first study period until the last blood draw in the final study period.
6. Any concomitant medication [prescription medications (e.g., prescription pills, topical systemic creams, inhalants, sprays [except for contraceptives]) or over-the-counter (e.g., acetaminophen, Ricola, oral multivitamins) (except for spermicidal/barrier contraceptive products)], any herbal and/or dietary supplements will not be permitted for 14 days prior to first study drug administration until the last blood draw in the final study period unless deemed otherwise by the PI/Sub-Investigator for treatment of any adverse events (AEs).

Any use of concomitant medication or herbal/dietary supplement during the restriction period will be reported as soon as possible to the PI/Sub-

Investigator, BPSI PK Scientist and/or the Sponsor. In each case, the decision whether to continue or discontinue the subject's participation in the study will be made by the PI/Sub-Investigator and/or by the BPSI PK Scientist and/or by the Sponsor.

7. The consumption of foods and/or beverages containing grapefruit and/or pomelo (e.g., grapefruit, grapefruit juice, grapefruit candies, pomelo, etc.) will be prohibited for 10 days prior to first study period until the last blood draw in the final study period.
8. The consumption of alcohol of any kind (e.g., wine, beer, liquor, cocktails), products containing caffeine/methylxanthines [e.g., coffee, tea, chocolate, caffeine-containing soft drinks (e.g., Coke, Pepsi, Red Bull)] and poppy seeds containing products (poppy seed cake, cookies, bagels) will be prohibited for 48 hours prior to study period until after the last blood draw in each study period.
9. Use of diuretics (drugs or food, see [Appendix D](#)) will be prohibited for 24 hours prior to SmartPill™ administration until after the last blood draw in each study period.
10. Physical activity: For the SmartPill™ administration (Study arm A and B on Day 2) (Study arm C and D on Day 7), subjects will remain awake and seated in an upright position for the first 4 hours following SmartPill™ administration where possible. Subjects are allowed to rise under supervision only for brief periods of time during the first 4 hours post-dose to assure subjects' safety and to use the washroom, after which they will be allowed to ambulate freely within the clinic. However, if a medical event (i.e. AE) occurs, subjects may be placed in an appropriate position at any time. Subjects will be required to abstain from strenuous activities for the duration of the study period(s).
11. For Study arm A and B on Day 2 and for Study arm C and D on Day 7, for 1 hour after each nifedipine administration, subject visits to the washroom will be monitored and recorded by clinic staff. Subjects will be restricted from flushing the toilet to allow staff to inspect the content during this time.

